#### **14.5 Sample Size Justification**

The phase I component of the trial will be conducted using a standard 3+3 dose escalation design. As there are four dose levels to be assessed (and two minus dose levels if needed), a total of 9-24 patients will be needed to complete the study.

In the phase II portion of the study, disease control rate is the primary endpoint and the study will be conducted using a Simon two-stage design. As outlined in section 14.2, a minimum of 18 and a maximum of 40 patients will be required.

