## PROTOCOL SUMMARY

Protocol Number/Title	CASE 1216: Phase I/II study of CB-839 and capecitabine in patients with advanced solid tumors and fluoropyrimidine resistant PIK3CA mutant colorectal cancer
Study Phase	Phase I/II
Brief Background/Rationale	Colorectal cancer is the third most common cause of cancer and second highest cause of cancer related death in the United States. Limited treatment options are available and the median overall survival is just over two years. Approximately 15-30% of colorectal cancers harbor a mutation in PIK3CA. Recent preclinical data suggest that PIK3CA mutant colorectal cancers may be more dependent on glutamine for growth and inhibition of glutamine metabolism with CB-839 inhibits growth. Additionally, treatment with CB-839 induces UPP1 gene expression and may potentiate the activity of fluoropyrimidines. In the phase I portion of this study, we will evaluate the safety, toxicity and pharmacokinetics of CB-839 and capecitabine chemotherapy in patients with advanced solid tumors for whom there are no further treatment options or for whom capecitabine is an acceptable treatment option. In the phase II portion of the study, we will evaluate the antitumor activity and survival benefit of combination CB-839 and capecitabine chemotherapy in patients with metastatic PIK3CA mutant colorectal cancer who are refractory to fluoropyrimidine based therapy, and will also explore the pharmacodynamics of this combination therapy in pre- and post-treatment blood and tissue specimens.
Primary Objective	
Phase I Primary Objective:
 
To determine the safety, tolerability and recommended phase II dose (RP2D) of combination CB-839 and capecitabine chemotherapy in patients with advanced solid tumors for whom there are no remaining treatment options or for whom single agent capecitabine is an acceptable therapy.
 
Phase II Primary Objective:
 
To determine the disease control rate of combination CB-839 and capecitabine chemotherapy in patients with metastatic PIK3CA mutant colorectal cancers who are refractory to fluoropyrimidine based therapy.

Secondary Objectives	
Phase I Secondary Objectives:
 
To determine the dose-limiting toxicities and maximum tolerated dose of combination therapy with CB-839 and capecitabine in patients with advanced solid tumors for whom there are no remaining treatment options or for whom single agent capecitabine is an acceptable therapy.

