### **2.1 Primary Objective**

- 2.1.1 Phase I: To determine the safety, tolerability and recommended phase II dose (RP2D) of combination CB-839 and capecitabine chemotherapy in patients with advanced solid tumors for whom there are no remaining treatment options or for whom single agent capecitabine is an acceptable therapy.
- 2.1.2 Phase II: To determine the disease control rate of combination CB-839 and capecitabine chemotherapy in patients with metastatic PIK3CA mutant colorectal cancers who are refractory to fluoropyrimidine based therapy.

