## **12.0 MEASUREMENT OF EFFECT**

Although response is not the primary endpoint of the phase I portion of this trial, patients will be assessed by standard criteria. Response rate is the primary endpoint for the phase II portion of the trial. For the purposes of this study, patients should be re-evaluated every 9 weeks in addition to undergoing a baseline scan.

Response and progression will be evaluated in this study using the new international criteria proposed by the revised Response Evaluation Criteria in Solid Tumors (RECIST) guideline (version 1.1) (23). Changes in the largest diameter (unidimensional measurement) of the tumor lesions and the shortest diameter in the case of malignant lymph nodes are used in the RECIST criteria.

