## **14.0 STATISTICAL CONSIDERATIONS**

### **14.1 Study Design/Endpoints**

#### **14.1.1 Definition of Primary Endpoint**

Phase I: Safety, tolerability and recommended phase II dose (RP2D) of combination therapy with CB-839 and capecitabine chemotherapy in patients with no remaining treatment options or patients for whom single agent capecitabine is an acceptable therapy.

Phase II: : Progression free survival (PFS) on combination CB-839 and capecitabine as determined by clinical assessment and RECIST criteria in patients with metastatic PIK3CA mutant colorectal cancer who are refractory to fluoropyrimidine based therapy. Progression free survival is defined as the time from randomization to documented progression or death without progression.

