## **14.2 Analytic Plan for Primary Objectives**

The phase I component of this study is a dose-escalation trial of CB-839 and capecitabine in patients with advanced solid tumors for whom there are no remaining treatment options or for whom capecitabine is an acceptable treatment. It has been designed to define the recommended phase II dose of CB-839 and capecitabine. A traditional 3+3 dose escalation design will be adopted. Nine to twenty-four patients are expected to be enrolled, depending on the number of dose escalations and assuming that a total of 6 patients will be treated at the final recommended phase II dose level. Patients who complete the first 21 day treatment cycle of CB-839 and capecitabine chemotherapy will be included in the analysis. Patients who do not complete the first 21 day treatment cycle or who fail to receive at least 75% of the doses of both CB-839 and capecitabine for reasons unrelated to toxicity will not be included and must be replaced.

In the phase II component of this study, the primary endpoint is progression free survival rate at 6 months with a null hypothesis of 18% vs. a target of 36%. Employing a 2-stage design, and assuming 80% power and a 0.05 significance level, 40 total patients will be required with 18 in the first stage and the probability of early stopping if the null hypothesis is correct (<3/18 patients with stable disease at 6 months) will be 0.589. If at least 3 patients in 18 has stable disease or better at 6 months, an additional 22 patients will be treated (total of 40 patients). If antitumor activity is identified in the PIK3CA mutant population, we will consider amending the phase 2 trial to assess an additional cohort of patients with wild-type PIK3CA. The statistical considerations will follow the same rules as in the original mutant cohort. Response rate will be determined using RECIST criteria.

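### The current text names conflicting phase II primary endpoints, and only the 6-month PFS rate carries the 18% versus 36% hypotheses behind the 18/40 design

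*Combined protocol and SAP*

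**What the plan says.** All of the following is current text, not the summary of changes.

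- **Disease control rate, no time point.** The phase II primary objective in the Protocol Summary is "To determine the disease control rate of combination CB-839 and capecitabine chemotherapy", and section 2.1.2 repeats it. Section 3.2 describes the single-arm design as assessing this rate. Section 14.5 says "disease control rate is the primary endpoint and the study will be conducted using a Simon two-stage design", then takes its 18 to 40 patients from section 14.2.
- **6-month PFS rate.** Section 14.2 says "the primary endpoint is progression free survival rate at 6 months with a null hypothesis of 18% vs. a target of 36" per cent, with 80% power, a 0.05 significance level, 18 patients in stage 1 and 40 in total. Its continuation rule reads "If at least 3 patients in 18 has stable disease or better at 6 months".
- **PFS as a time.** Section 14.1.1 makes PFS the primary endpoint without a landmark: "Progression free survival is defined as the time from randomization to documented progression or death without progression". The Summary and section 2.2.2 list PFS as a secondary objective. Section 12.5 counts PFS from start of treatment.
- **Response rate.** Section 12.0 says "Response rate is the primary endpoint for the phase II portion of the trial". Section 14.1.2 lists response rate as secondary.

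Disease control rate does not appear among the endpoint definitions in sections 14.1.1 to 14.1.3. In the response criteria, the only timing attached to stable disease is in the best-overall-response table of section 12.4, which accepts it if documented once at 8 weeks or later.

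**The concern.** A two-stage rule has known error rates only for the endpoint whose null and target were used to build it. Section 14.2 supplies these for the 6-month PFS rate and for nothing else. A reader who follows section 14.5 or 12.0 applies the same 18/40 rule to an endpoint with no stated null or target.

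The direction of the error depends on the reading. A patient who is progression-free at 6 months was also controlled at the earlier scans, while some patients controlled at week 9 will have progressed by 6 months. Best-response disease control therefore cannot be lower than the 6-month rate, and the chance of passing an inactive regimen can only rise. With response rate, which excludes stable disease, the same rule becomes very hard to pass. In a single-arm trial this rule is the main safeguard on the conclusion, so its endpoint should not be open to choice once data are in.

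**Working it through.** **Inputs.** From section 14.2: p0 = 0.18, p1 = 0.36, n1 = 18, N = 40, alpha 0.05 (taken as one-sided, as is usual for a Simon design) and power 0.80. The plan states no final cutoff, so it has to be derived.

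**Formulas** (exact binomial; b is the binomial probability, r1 the largest stage 1 count that stops the trial, c the final cutoff):

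- P(stop) = Σ b(x; 18, p) for x = 0 to r1
- P(pass) = Σ b(x; 18, p) × P[Bin(22, p) ≥ c − x] for x = r1 + 1 to 18

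**1. The plan's own figures.** At p = 0.18 the probabilities of 0, 1, 2 and 3 successes in 18 are 0.0281, 0.1110, 0.2071 and 0.2425. Stopping at ≤2/18, as printed, gives 0.346. Adding the fourth term gives 0.589. Section 14.2 states "the probability of early stopping if the null hypothesis is correct (<3/18 patients with stable disease at 6 months) will be 0.589", so the printed probability belongs to stopping at ≤3/18. Both bounds are carried below.

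| Final cutoff | Stop ≤2/18: alpha, power | Stop ≤3/18: alpha, power |
|---|---|---|
| ≥11/40 | 0.089, 0.896 | 0.081, 0.869 |
| ≥12/40 | 0.0439, 0.826 | 0.0415, 0.807 |
| ≥13/40 | 0.0195, 0.729 | 0.0188, 0.717 |

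Only ≥12/40 meets both limits. N = 40 therefore reproduces for the 6-month PFS rate under either bound.

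**2. Disease control counted at 6 months.** This is nearly the same quantity as the 6-month PFS rate. With an 18% null, alpha is 0.041 to 0.044 and the design fits.

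**3. Disease control as best overall response.** The documents give no null for this, so the rates are assumptions. P(pass) for an inactive regimen with ≥12/40:

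| Assumed null | Stop ≤3/18 | Stop ≤2/18 |
|---|---|---|
| 30% | 0.54 | 0.55 |
| 35% | 0.77 | 0.79 |
| 40% | 0.91 | 0.93 |
| 50% | 0.994 | 0.996 |

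The plan's 18% at 6 months (26.09 weeks) can also be carried back to week 9. With a Weibull curve of shape k, S(9) = 0.18^((9/26.09)^k). P(pass) uses stop at ≤3/18:

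| Shape k (assumed) | S(9) | P(pass) |
|---|---|---|
| 0.5 | 0.365 | 0.82 |
| 0.8 | 0.481 | 0.989 |
| 1.0 (constant hazard) | 0.553 | 0.999 |
| 2.0 | 0.815 | >0.999 |

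Assuming equal risk per scan interval instead gives 0.18^(1/2) = 0.424 and P(pass) 0.95 with two intervals to 6 months, or 0.18^(1/3) = 0.565 and 0.999 with three.

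**4. Response rate.** At assumed true response rates of 10%, 15% and 20%, P(pass) with stop at ≤3/18 is below 0.001, 0.011 and 0.08.

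**5. Time-to-event PFS.** Section 14.1.1 gives no null, target or test for PFS as a time, so neither alpha nor power can be computed for it.

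**The case against.** The strongest reply is that section 14.2 governs. Its heading marks it as the analysis plan for the primary objectives, and it fixes the endpoint, null, target and stage 1 count. Section 14.5 refers to it for the sample size, and its stage 1 rule counts stable disease or better at 6 months, which is disease control at that time. Section 14.1.1 can be read as defining the PFS variable and section 14.2 as setting the landmark, which would leave three labels rather than four. No section ties the primary disease control rate to best overall response, and the pass probabilities under that reading rest on assumed nulls.

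Much of this is fair. Disease control at 6 months fits the design, the sample size is not wrong, and the false-positive figures are illustrations. Merging 14.1.1 with 14.2 is reasonable.

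The conflict remains after these concessions. Three different primaries are still named, and section 12.0's response rate cannot be reconciled with 14.2 on any reading. No section attaches a 6-month time point to the disease control rate that the objectives call primary. The best-response reading stays open because the protocol's response criteria tie no other timing to stable disease.

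**Conclusion.** The concern holds. The phase II primary endpoint is not uniquely named, and the 18/40 design belongs to one candidate only, the 6-month PFS rate. For that endpoint, and for disease control at 6 months, the error rates are as intended (alpha 0.041 to 0.044, power 0.81 to 0.83, with the derived cutoff of 12/40).

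Under best-response disease control the chance that an inactive regimen passes is at least 0.54 for assumed nulls of 30% or more, and at least 0.82 when the plan's 18% is carried back to week 9 under the assumed curves. Under response rate the chance of passing is about 0.08 or less for true rates up to 20%. The existence of the conflict and the upward direction of the best-response error do not depend on these assumptions; the sizes do. This should be fixed before the phase II result is analysed.

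**What to change.** Name one phase II primary endpoint everywhere: the proportion alive and progression-free (CR, PR or SD) at 6 months from start of treatment.

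- Change the Protocol Summary, 2.1.2, 3.2 and 14.5 to this endpoint.
- In 14.1.1 add the 6-month landmark and count from start of treatment, as 12.5 does, since a single-arm phase II has no randomization.
- Correct the response-rate sentence in 12.0.
- State which scan decides 6-month status, because scans fall near weeks 9, 18 and 27.
- Keep time-to-event PFS, overall survival and response rate as secondary, and label the PFS in the Summary and 2.2.2 as time-to-event. Best-response disease control is not a listed secondary endpoint; if it is wanted, add it as one with its own definition.
- In the same edit, reconcile the stage 1 rule in 14.2 with its stated early-stopping probability (0.346 for <3/18, 0.589 for ≤3/18) and state the final success cutoff.

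The cost is consistency edits in one amendment. No new patients or data are needed.

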#### **14.6 Accrual Rate Estimate**

Accrual for this study will occur at the University Hospitals Seidman Cancer Center and the Cleveland Clinic Taussig Cancer Institute, both of the Case Comprehensive Cancer Center. For the phase I portion of the trial, we anticipate that it will take approximately 6-7 months to complete this portion of the trial if all doses levels need to be evaluated. For the phase II portion of the study, between the two institutions, 719 colorectal cancer patients are seen annually. We estimate that approximately 30% of our patients will have measureable, metastatic disease and that 15% of patients will have a PIK3CA mutation, resulting in 32 eligible patients per year. Based on our proposed sample size of 18-40 patients, we anticipate that it will take approximately 18-40 months to accrue to the phase II portion of the trial.

**APPENDIX I**  
**PERFORMANCE STATUS CRITERIA**

ECOG Performance Status Scale		Karnofsky Performance Scale	
Grade	Description	Percent	Description
0	Normal activity. Full active, able to carry on all pre-disease performance without restriction.	100	Normal, no complaints, no evidence of disease.
		90	Able to carry on normal activity; minor signs or symptoms of disease.
1	Symptoms, but ambulatory. Restricted in physically strenuous activity, but ambulatory and able to carry out work of a light or sedentary nature (e.g., light housework, office work).	80	Normal activity with effort; some signs or symptoms of disease.
		70	Cares for self, unable to carry on normal activity or to do active work.
2	In bed < 50% of the time. Ambulatory and capable of all self-care, but unable to carry out any work activities. Up and about more than 50% of waking hours.	60	Requires occasional assistance, but is able to care for most of his/her needs.
		50	Requires considerable assistance and frequent medical care.
3	In bed > 50% of the time. Capable of only limited self-care, confined to bed or chair more than 50% of waking hours.	40	Disabled, requires special care and assistance.
		30	Severely disabled, hospitalization indicated. Death not imminent.
4	100% bedridden. Completely disabled. Cannot carry on any self-care. Totally confined to bed or chair.	20	Very sick, hospitalization indicated. Death not imminent.
		10	Moribund, fatal processes progressing rapidly.
5	Dead.	0	Dead

## **APPENDIX II**

### **PATIENT PILL DIARY FOR TWICE DAILY DOSING OF CB-839 (WHILE TAKING WITH CAPECITABINE)**

Patient Name \_\_\_\_\_ Patient Study ID \_\_\_\_\_ Todays date \_\_\_/\_\_\_/\_\_\_  
Drug \_\_\_\_\_ Cycle #:\_\_\_\_\_

#### **INSTRUCTIONS FOR THE PATIENT:**

1. Complete one form every 3 weeks (one treatment cycle).
2. You will take CB-839 tablets twice each day about 12 hours apart. Each dose should be taken with food—the first dose of the day should be taken with breakfast, the second dose of the day should be taken with dinner.  
Morning dose: take \_\_\_ 200 mg capsules  
Evening dose: take \_\_\_ 200 mg capsules
3. Record the date, the number of capsules that you took, and what time you took them.
4. If you have any comments or notice any side effects, please record them in the “Comments” column.
5. Please bring this form and your bottle(s) of CB-839 to your physician when you return for each appointment.
6. Please sign your name at the bottom of the diary.

Day	Date	Time of morning dose	# of tablets taken		Time of evening dose	# of tablets taken		Comments
			200 mg			200 mg		
1								
2								
3								
4								
5								
6								
7								
8								
9								
10								
11								
12								
13								
14								
15								
16								
17								
18								
19								
20								
21								

Patient's Signature: \_\_\_\_\_ Date: \_\_\_\_\_

### **APPENDIX III**

#### **PATIENT PILL DIARY FOR TWICE DAILY DOSING OF CAPECITABINE (WHILE TAKING WITH CB-839)**

Patient Name \_\_\_\_\_ Patient Study ID \_\_\_\_\_ Todays date \_\_\_/\_\_\_/\_\_\_  
Drug \_\_\_\_\_ Cycle #:\_\_\_\_\_

##### **INSTRUCTIONS FOR THE PATIENT:**

1. Complete one form every 3 weeks (one treatment cycle).
2. You will take capecitabine tablets twice each day about 12 hours apart. Each dose should be taken within 30 minutes of eating breakfast and within 30 minutes of eating dinner.  
Morning dose: take \_\_\_ 500 mg tablets  
Evening dose: take \_\_\_ 500 mg tablets
3. Record the date, the number of tablets that you took, and what time you took them.
4. If you have any comments or notice any side effects, please record them in the "Comments" column.
5. Please bring this form and your bottle(s) of capecitabine to your physician when you return for each appointment.
6. Please sign your name at the bottom of the diary.

Day	Date	Time of morning dose	# of tablets taken		Time of evening dose	# of tablets taken		Comments
			500 mg			500 mg		
1								
2								
3								
4								
5								
6								
7								
8								
9								
10								
11								
12								
13								
14								
15								
16								
17								
18								
19								
20								
21								

Patient's Signature: \_\_\_\_\_ Date: \_\_\_\_\_

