### **3.3 Replacement of Patients**

3.3.1 Phase I: If a patient is withdrawn from the study for any reason other than a dose limiting toxicity prior to completing the first 21 days of combination therapy with CB-839 and capecitabine, a replacement patient will be enrolled and will be assigned to the same dose level.

Unless the patient has had their study drug held for an adverse event that may herald a DLT, if a patient does not take at least 75% of the planned doses of each of the two agents (CB-839 and capecitabine), the patient will be replaced because he/she has not taken enough drug to confirm safety at that dose level.

3.3.2 Phase II: If a patient does not take at least 75% of the planned doses of each of the two agents (CB-839 and capecitabine) prior to the first disease assessment (9 weeks), the patient will be replaced because he/she has not taken enough drug to assess efficacy.

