#### **6.2.2 Capecitabine Administration**

Patients will receive capecitabine chemotherapy orally by mouth twice daily for the first 14 days of each 21 day treatment cycle. During the phase I component of the study, the dose of capecitabine administered will be dictated by the dose escalation table. During the phase II component of the study, the dose of capecitabine administered will be 1000 mg/m^2 twice daily on days 1-14 of a 21 day treatment cycle as was determined during the phase I component of the study.

Capecitabine tablets should be taken whole with water within 30 minutes following a meal. Doses will be taken approximately 12 hours apart at the end of a meal.

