## 7.2 Capecitabine Dose Modifications

Capecitabine will be initiated at the dose per the assigned dose level and will be given twice daily for the first 14 days out of a 21 day treatment cycle.

Dose modifications should be made according to the following table:

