f Pharmacokinetic sample should be drawn just prior to the administration of the morning dose of CB-839 and capecitabine.

g Restaging CT scans may be performed +/- 7 days at all timepoints beyond the cycle 3 evaluation.

h Treatment starts this day. CB-839 is to be taken twice daily continuously (21/21 days) and capecitabine is to be taken twice daily for 14/21 days).

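### The capecitabine patient diary (Appendix III) gives a twice-daily instruction on a 21-day form and names no dosing days, whereas section 6.2.2 gives capecitabine on days 1 to 14 only

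*Combined protocol and SAP*

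**What the plan says.** Appendix III is titled as a diary for twice-daily capecitabine taken alongside CB-839. Its first instruction asks for one form per three-week treatment cycle. Its second reads "You will take capecitabine tablets twice each day about 12 hours apart", ties each dose to breakfast or dinner, and leaves blanks for the number of 500 mg tablets in the morning and evening. The table has a row for each of days 1 to 21, with columns for both doses.

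The body of the protocol states the schedule differently:

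- Section 6.2.2: "Patients will receive capecitabine chemotherapy orally by mouth twice daily for the first 14 days of each 21 day treatment cycle". For phase II it repeats the days: "twice daily on days 1-14 of a 21 day treatment cycle as was determined during the phase I component of the study".
- Section 7.2: capecitabine "will be given twice daily for the first 14 days out of a 21 day treatment cycle".
- Section 11.4, phase II calendar footnote: "CB-839 is to be taken twice daily continuously (21/21 days) and capecitabine is to be taken twice daily for 14/21 days".
- Section 3.2 (phase II design), section 6.1.2 and the treatment-period lists in section 11.2.2 also give 14 of 21 days.

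Appendix II, the CB-839 diary, has the same twice-daily sentence with the drug name changed and the same 21-row table. Section 9.2 names the Appendix III diary under drug accountability for capecitabine and names no other measure there.

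**The concern.** The diary carries a dosing instruction that the patient takes home. It gives how often to take the drug and how far apart, but not on how many days. The treatment plan makes the number of days part of the regimen, and section 1.4 states the recommended phase II dose on a days 1 to 14 schedule. A patient holding both diaries sees nothing to distinguish the drug taken continuously from the drug taken for two weeks in three.

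The stake is patient safety: a cytotoxic drug might be taken in a week when the treatment plan gives none. The check on capecitabine amount in section 6.2 limits the total daily dose to 105% of the calculated dose. Extra days at the correct daily dose would not breach that limit. Section 8.3.3 makes a dose above the protocol's reportable even without an adverse event, so the form could also lead to reportable overdoses.

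**Working it through.** **Inputs.** Phase II capecitabine dose: 1000 mg/m² twice daily (6.2.2). Dosing days in the treatment plan: 14 per cycle (6.2.2, 7.2, 11.4). Days with dose entries on the diary: 21 (Appendix III). Worked example: body surface area 1.97 m² (6.2).

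**The plan's own figure.** The documents state no total dose per cycle. They do give a daily example, which reproduces:

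- Daily dose = 2 × 1000 × 1.97 = 3940 mg, as stated.
- Rounded up: 4000 / 3940 − 1 = +1.5%, as stated.
- Rounded down: 3500 / 3940 − 1 = −11.2%, stated as 11% lower.

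**Doses per cycle.** Doses = 2 × dosing days.

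| | Treatment plan (6.2.2) | Diary read literally |
|---|---|---|
| Dosing days | 14 | 21 |
| Doses per cycle | 2 × 14 = 28 | 2 × 21 = 42 |
| mg/m² per cycle at 1000 mg/m² | 28 × 1000 = 28,000 | 42 × 1000 = 42,000 |
| mg per cycle at 4000 mg/day | 14 × 4000 = 56,000 | 21 × 4000 = 84,000 |

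Excess = 42 − 28 = 14 doses, or 14,000 mg/m². Ratio = 42 / 28 = 1.50, so +50%. The ratio depends only on 21/14 and is the same at 500, 750 or 1000 mg/m².

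**Scheduled contacts that might reveal continued dosing.** In phase II, cycle 1 has visits on days 8 and 15. From cycle 2 the only scheduled clinic assessment is day 1, apart from a restaging CT late in cycle 3 and then every nine weeks (11.2.2, 11.4). The day 15 visit lists symptoms and laboratory tests and does not list a diary check. The documents give no number of capecitabine tablets to be dispensed per cycle, and section 9.2 describes capecitabine as commercially available at the patient's cost.

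**The case against.** The strongest reply is that the diary omits something but does not set a rival schedule. Its instruction describes frequency and spacing. The three-week statement says how often to complete a form. The rows ask for what was taken, so they can hold blanks in the off week and would expose doses taken in error. Staff who fill in the tablet counts work from a protocol body that is consistent on 14 of 21 days. Patients bring the form and bottles to each appointment, and cycle 1 has a visit on day 15. Shading or crossed-out cells in rows 15 to 21 could have been lost when the PDF was read. Prescription labels and quantities dispensed are not in the documents, and the consent pages were removed.

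Much of this stands. A reader might infer that Appendix III orders capecitabine on days 15 to 21, or that patients who use it will take 50% more. The documents do not support either: the form gives a frequency without a duration, and other instructions may fill the gap. What the reply does not remove is that the printed instruction leaves out a part of the regimen that section 6.2.2 states expressly, on a form worded like that of a continuously dosed drug. The safeguards visible in the plan also thin out after cycle 1.

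A reader might also infer that the diary undermines the 75% rules, because a fully adherent patient fills 28 of 42 slots, or 66.7%. That does not hold. Section 3.3.2 replaces a phase II patient "if a patient does not take at least 75% of the planned doses of each of the two agents", so the denominator is already planned doses. Section 6.4 likewise counts planned administrations, and it governs evaluability for dose-limiting toxicity in phase I, which section 1.4 describes as fully accrued by January 2018. No section uses diary rows as a denominator.

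**Conclusion.** The point holds as a patient-safety inconsistency between a patient-facing form and the treatment plan. Appendix III, as its text can be read here, names neither dosing days nor a rest period; section 6.2.2 and the other treatment sections give days 1 to 14. The possible consequence is at most 42 doses per cycle against 28, or +50%. That maximum assumes the patient doses on every printed row, that no marking on the original form blocks rows 15 to 21, and that no label, tablet supply or verbal instruction intervenes. The documents neither confirm nor exclude these conditions, so neither the frequency of the error nor actual harm can be estimated from them. The trial's endpoints, sample size and replacement rule are not affected on this ground.

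**What to change.** Reconcile Appendix III with section 6.2.2. The diary's instruction should name the capecitabine dosing days, and the rows with dose entries should match them, so that the form and the treatment plan show the same days. If the remaining rows are kept to record days without a dose, the form should say so. The sponsor should also check whether the original form carries markings that the available text does not show. No dose or schedule is proposed here, and the 75% rule needs no rewording.

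The cost is a revised one-page diary submitted with the next amendment. It needs no extra patients, visits or procedures.
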